Union Rate of Transverse Tibia Fracture

NCT03042533

Date: 09.05.23

Union Rates of Transverse Tibia Fractures Managed with Internal Fracture Compression Through an Intramedullary Rod Compared to Standard “Backslapping”

[name]

Introduction

When compared to other fracture patterns, transverse fractures of the tibial shaft have historically been associated with an increased incidence of delayed union and nonunion when stabilized with intramedullary rods, perhaps due to the decreased cortical surface area available for healing.¹⁻⁴ As a result, some authors have recommended that simple transverse fractures of the tibial shaft be managed with plate fixation and compression of the fracture using an articulated dynamic tensioner.⁵ Open plating of the tibia requires a large incision which may be at an increased risk for soft tissue complications, particularly when operating through a high-energy injured soft tissue envelope. Furthermore, intramedullary rodding of the tibia is currently regarded as the gold standard for surgical management of tibia fractures, including transverse fractures, and as such compression plating is not considered a reasonable option unless other mitigating circumstances exist.¹

In recent years, technological advances in the design of intramedullary rods allow intraoperative, controlled compression of fractures with internal devices built in to the rod. This type of controlled compression may be beneficial when compared to traditional “backslapping” techniques, in which the amount of compression cannot be controlled or “dialed” in. After internal compression, static or dynamic locking of the rod can be accomplished as is routine when rodding typical long bone fractures. This advance poses a potential advantage when managing transverse fractures, the one fracture type most amenable to intraoperative compression to facilitate rapid bony healing.

The literature regarding intramedullary rodding of transverse tibia fractures is limited, and no literature exists comparing controlled internal compression with traditional methods of dynamic rodding or backslapping. The purpose of this analysis is to prospectively assess a consecutive cohort of patients with transverse tibial shaft fractures treated with intramedullary rodding and compressed with one of three methods: dynamic locking alone, backslapping followed by dynamic locking locking, or controlled internal

fracture compression with modern nails followed by static locking.

Primary Hypothesis:

Our hypothesis is that internal, controlled transverse fracture compression with modern intramedullary rod treatment of transverse tibial shaft fractures will be associated with an increased rate and time to union compared to the traditional methods of dynamic locking and backslapping.

Methods:

Inclusion Criteria

1. Skeletal Maturity
2. Closed or open diaphyseal (shaft) tibia fracture that is axially stable and will tolerate compression without shortening.
3. Treatment with Intramedullary Rod.
4. Fracture compression using one of three methods:
 - a. Dynamic locking.
 - b. Backslapping with dynamic locking.
 - c. Internal rod compression with static locking.
5. Complete inpatient and outpatient medical records and operative notes.
6. Complete radiographic and clinical follow-up for minimum one year.

Exclusion Criteria

1. Skeletally immature.
2. Metabolic Bone Disease
3. Immunosuppression
4. Pathological Fracture (Tumor, Pre-existing Infection)
5. Pre-existing Infection
6. Soft-tissue coverage not obtained within two weeks from time of injury.
7. Use of Negative Pressure Dressing to definitively manage wound.
8. Use of external or implantable bone growth stimulator.

9. Unable to Full Weight Bear immediately post-operative.

Data Points:

1. Age
2. Sex
3. Medical Comorbidity
4. Smoking Status (Yes or No)
5. Closed or Open fracture:
 - a. Wound Size (surface area)
 - b. Wound type (Gustilo Anderson and OTA)
6. Number of Surgical Debridements
7. Time to definitive closure.
8. Soft Tissue Reconstructive Procedure
9. Compartment Syndrome (Yes or No)
10. Fasciotomy (Yes or No)
11. Treatment Method:
 - a. Dynamic locking.
 - b. Backslapping with dynamic locking.
 - c. Internal rod compression with static locking.
12. Union (Yes or No)
13. Time to union (months).
14. Implant complications (Rod or Screw Breaking)
15. Loss of reduction and healing alignment on orthogonal radiographs.
16. Need for subsequent secondary treatment:
 - a. Superficial Infection (Antibiotic Treatment)
 - b. Deep Infection (Surgical Treatment)
 - c. Delayed Union (Exchange rodding, Bone grafting)
 - d. Nonunion (Exchange rodding, Bone grafting)

Methodology:

This study will be a prospective analysis of patients with transverse tibial shaft fractures (OTA 42-A3 classification) treated with an intramedullary rod. Patients will be enrolled at a single facility (Harborview Medical Center-HMC). Patients who meet inclusion criteria will be assigned to one of the three treatment groups based on the night of presentation. Currently there are three teams that manage the trauma call at HMC (Red, Green, Blue) and alternate on a strict 1 in 3 rotation schedule. Patients that present on a night when the Red Team is on call will be treated as Group A (dynamic locking). Patients that present on a night when the Green Team is on call will be treated as Group B (backslapping with dynamic locking). Patients that present on a night when the Blue Team is on call will be treated as Group C (internal rod compression). All three methods of treatment are considered acceptable current standards of practice in the orthopedic trauma community on a local and national level. All patients will be treated similarly with respect to:

1. Open wound management
2. Immediate post-operative full weight bearing.
3. Follow-up at 6 weeks, 12 weeks, 24 weeks and 52 weeks.
 - a. Radiographic
 - b. Clinical

Union will be determined according to the modified Hammer criteria,⁶ with union considered to have occurred with bridging cortical bone on 3 or 4 cortices using orthogonal radiographic views.

Risks

There is no risk to the patient as all three treatment methods are current standard of practice both nationally and locally. All patient identifiers will be kept private. All data will be stored on a password protected database available only to the study team.

Benefits

The study performed will provide information regarding the optimal treatment strategy for transverse tibia fractures, and what the expected time to union is when using internal

compression. This information is of benefit to patients, particularly when being counseled by surgeons regarding how long they can expect before obtaining radiographic union, and what the potential reoperation rate would be.

Procedures to Ensure Confidentiality

No patient identifiers will be used during the formal study. Identifiers such as name and medical record numbers will be used to identify patients with a transverse tibia fracture, and will be stored on a password protected departmental network in a master file. Data files will be listed with subject number.

Statistical Analysis Plan

Descriptive statistics will be presented as means and standard deviations for continuous variables and as frequencies and percentages for categorical variables. Statistical analysis of categorical variables utilized Fischer's exact test with descriptive statistics reported as frequencies and percentages. For continuous variables, a Mann-Whitney U test was utilized with descriptive statistics reported as means and ranges. Significance set at p value less than or equal to 0.05. All statistical analyses were performed using IBM SPSS version 22 (Chicago, IL, 2013).

Bibliography:

1. Randomized Trial of Reamed and Unreamed Intramedullary Nailing of Tibial Shaft Fractures. *J Bone Joint Surg Am.* 2008;90:2567-2578.
3. Court-Brown CM. Reamed Intramedullary Tibial Nailing: An Overview and Analysis of 1106 Cases. *J Orthop Trauma.* 2004;18:96-101.
4. Blachut PA O'Brien PJ, Meek RN, Broekhuyse HM. Interlocking Intramedullary Nailing With and Without Reaming for the Treatment of Closed Fractures of the Tibial Shaft. *J Bone Joint Surg Am.* 1997;79:640-646.
6. Hammer RR Hammerby S, Lindholm B. Accuracy of Radiographic Assessment of Tibial Shaft Fracture Union in Humans. *Clin Orthop Relat Res.* 1985;199:233-238.

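### The primary hypothesis joins union rate and time to union against two comparators with no primary endpoint, testing order or multiplicity rule, and its wording on time to union points the wrong way

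*Combined protocol and SAP*

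**What the plan says.** The Primary Hypothesis section states that internal controlled compression "will be associated with an increased rate and time to union compared to the traditional methods of dynamic locking and backslapping". One adjective governs both rate and time, and two comparator methods are named.

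The Introduction gives the rationale. Transverse tibial fractures have been "associated with an increased incidence of delayed union and nonunion when stabilized with intramedullary rods". Of the newer rods it says "This type of controlled compression may be beneficial when compared to traditional" backslapping, and it calls the transverse pattern "the one fracture type most amenable to intraoperative compression to facilitate rapid bony healing".

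The Data Points list holds the two outcomes separately: item 12 is union as a yes/no variable, and item 13 is time to union in months. The Methodology section sets follow-up at 6, 12, 24 and 52 weeks.

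On testing, the Statistical Analysis Plan says "Statistical analysis of categorical variables utilized Fischer's exact test" and "For continuous variables, a Mann-Whitney U test was utilized", with significance at p of 0.05 or less. It does not say which outcome is primary, which pairs of groups are compared, in what order, whether tests are one- or two-sided, or how error is controlled over several tests.

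**The concern.** A primary hypothesis should tell the reader what result would count as success. This one does not.

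- **Two endpoints, unranked.** Suppose internal compression shortens time to union but the proportions united are alike, or the reverse. The plan does not say whether the hypothesis is then supported, half supported or rejected.
- **Two comparators, unranked.** The same gap opens if internal compression beats backslapping but not dynamic locking. The plan does not say whether one win suffices or both are needed, or whether the two traditional methods are to be pooled.
- **Freedom to choose.** With each test at 0.05 and no order, any one significant result can become the headline afterwards, and the trial's false-positive rate is above 5%.
- **Direction.** An increased time to union is slower healing. The sentence against which the trial is judged thus conflicts with the reason given for doing it.

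**Working it through.** **1. Direction, by comparing the texts.** The Introduction treats delayed union and nonunion as the problem and rapid healing as the aim, which implies a shorter time to union. The hypothesis literally says longer. Rate could mean the proportion united or the speed of union. Reading it as speed does not help, because the sentence would then predict both faster union and a longer time to it. No later section corrects the wording.

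**2. Primary endpoint, by search.** The hypothesis, the Data Points list, the Methodology section and the Statistical Analysis Plan designate none. The title speaks of union rates, which leans towards the proportion united. The Benefits section stresses the expected time to union. Neither settles it.

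**3. Number of tests.** The documents give no sample size, expected union proportion or error calculation, so there is no figure of the plan's own to reproduce. Taking the hypothesis as internal compression against each traditional method: 2 endpoints × 2 comparators = 4 tests.

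**4. Simple bounds.** For k independent tests at 0.05, the chance of at least one false positive is 1 − (1 − 0.05)^k; the Bonferroni bound is 0.05k.

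| k | Case | Independent tests | Bonferroni bound |
|---|---|---|---|
| 1 | one endpoint, one comparison | 0.05 | 0.05 |
| 2 | two endpoints, one comparison | 0.0975 | 0.10 |
| 4 | two endpoints, two comparisons | 0.1855 | 0.20 |

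The 0.1855 is too high for this design. The two comparisons share the internal-compression arm, and Fisher's exact test falls below its nominal level with small counts.

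**5. Simulation under no difference.** Assumptions, none from the documents: equal arms, a common union probability, a common distribution of time to union, the two endpoints independent, 4000 replicates. Each replicate ran Fisher and Mann-Whitney tests of internal compression against dynamic locking and against backslapping.

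At 50 per arm and 90% union:

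| Tests | Chance of at least one p ≤ 0.05 |
|---|---|
| all four | 0.114 (other runs 0.119 and 0.13) |
| time to union only, two comparators | 0.087 |
| both endpoints, one comparator | 0.065 |
| one Fisher test | about 0.016 |

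Over 25 to 100 per arm and 80% to 90% union, all four tests gave about 0.11 to 0.15 in one set of runs and 0.10 to 0.14 in another. Time to union alone against two comparators gave 0.08 to 0.09. The proportion united alone against both gave 0.01 to 0.06.

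**6. Where the excess comes from.** In the 50-per-arm case the excess over 0.05 is 0.114 − 0.05 = 0.064. Time to union against two comparators already accounts for 0.087 − 0.05 = 0.037, or 0.037 / 0.064 = 58%. Adding the union endpoint contributes the remaining 0.114 − 0.087 = 0.027.

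**7. Effect of the independence assumption.** A fracture that has not united has no time to union, so the endpoints are linked. Correlation would generally bring the figure below those simulated.

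**The case against.** The strongest reply is that the direction is a slip of the pen. The Introduction makes the intent plain and no section mentions one-sided testing. If the tests are two-sided, correcting the word changes no statistic, p-value or estimate. This stands. A reader might infer that the trial expects slower healing, or that the sign of an endpoint is reversed in the analysis. The documents support neither: time to union in months carries no sign, and only the wording of the hypothesis does. What remains is that sidedness is unstated. Under a one-sided test, the literal wording would put the rejection region on the wrong side.

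A second reply is that no endpoint is labelled primary, so calling the two outcomes co-primary is an inference, and the title points to the union proportion. That is fair, but a leaning in a title is not a designation.

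A third reply concerns the size. A reader might take the whole excess in false positives as the price of joining two endpoints. That is not supported: much of it arises from the three-arm design with two comparators, as step 6 shows. The sample sizes and union proportions are also assumptions, and independence is implausible. The range is therefore an illustration, not a property that can be read off the plan.

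None of these replies supplies a primary endpoint, a set of comparisons or an order of testing.

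**Conclusion.** The point holds, and its main part is the undefined success criterion: two endpoints and two comparators in one hypothesis, each test at 0.05, with no ranking or error control. The size is a chance of about 11% to 15% of at least one false positive over four tests, against a nominal 5%. It rests on assumed arms of 25 to 100, union of 80% to 90% and independent endpoints. The two comparators contribute much of it, and the true figure is probably lower because the endpoints are related.

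The direction of the wording is a lesser fault, probably clerical, with no effect on two-sided p-values. It must still be corrected because it stands in the trial's only formal hypothesis.

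This should be repaired, but it does not show that any planned test is computed wrongly or in the wrong direction.

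**What to change.** In the Primary Hypothesis section, state that internal compression is expected to give a higher proportion united by 52 weeks (primary, in line with the title) and a shorter time to union (key secondary), each against backslapping and against dynamic locking.

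In the Statistical Analysis Plan, state that all tests are two-sided and give the order. One workable order is:

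1. proportion united, internal compression versus backslapping (the comparator in the title);
2. proportion united, versus dynamic locking;
3. time to union, versus backslapping;
4. time to union, versus dynamic locking.

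Each is tested at 0.05 only if the one before it succeeded. Holm's method across the comparisons is an alternative. Naming the comparisons matters as much as naming the endpoint, because ranking the endpoints alone would leave it unclear when the primary has been met.

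The cost is one sentence in the protocol and a short paragraph in the analysis plan. Treatment, visits and data collection are unchanged, since both outcomes are already recorded and the 52-week visit is scheduled. The real downside is that time to union becomes formally secondary. If union is high in all arms, the proportion has little room to differ and time to union could not be claimed as confirmatory. If the sponsor prefers time to union as primary, the same rule applies with the endpoints swapped.

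Parts of the analysis plan are written in the past tense, so it is unclear whether outcomes have been examined. If they have, the clarification should be dated and labelled as made afterwards, and all four comparisons reported.

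### Patients are assigned by call team, but eligibility and the recorded grouping run on the method used, and no analysis set is named, so selective departures from assignment could bias the comparison

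*Combined protocol and SAP*

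**What the plan says.** Four parts of the combined protocol and SAP bear on this point.

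- **Methodology (allocation).** "Patients who meet inclusion criteria will be assigned to one of the three treatment groups based on the night of presentation". The three teams "alternate on a strict 1 in 3 rotation schedule". Red nights give Group A and Green nights Group B; for Blue nights the text reads "Patients that present on a night when the Blue Team is on call will be treated as Group C (internal rod compression").
- **Methods, Inclusion Criteria.** Item 3 requires intramedullary rod treatment. Item 4 requires "Fracture compression using one of three methods": dynamic locking; backslapping with dynamic locking; or internal compression with static locking.
- **Methods, Data Points.** There are 16 items. Item 11, "Treatment Method", offers the same three options as inclusion item 4. No item is the call team, the assigned group, or the date or night of presentation.
- **Statistical Analysis Plan.** It names a test for categorical variables ("Statistical analysis of categorical variables utilized Fischer's exact test with descriptive statistics reported as frequencies and percentages"), a test for continuous variables and a significance level. It does not say whether patients are grouped by assigned team or by method used, and it has no rule for patients who receive a method other than their team's.

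**The concern.** The call rotation is what keeps the surgeon's view of an individual fracture from deciding which method is used. That protection lasts only if patients are analysed in the group the rotation gave them. Here the allocation rule runs on the team, while the eligibility rule and the only grouping field run on the method.

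The order is also circular: patients who meet the inclusion criteria are to be assigned, yet items 3 and 4, read literally, can be met only once the operation that follows assignment has been done.

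If departures from the team's method are related to how difficult the fracture is, excluding those patients or counting them under another method changes the case mix of the groups being compared. A difference in union could then appear without any effect of the method.

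**Working it through.** The documents state no sample size, effect size or crossover rate, so there is no figure to reproduce. The check has two parts.

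**1. Text check: what happens to a Blue-night patient (assigned to C)**

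| Treatment received | Inclusion items 3 and 4 | Data point 11 | Consequence |
|---|---|---|---|
| Internal compression, static locking | met | c | in C either way |
| Dynamic locking only | met | a | if item 11 records the method delivered, counted with Red-night patients; departure not visible |
| Rod, but none of the three listed combinations | item 4 not met | no option fits | excluded after allocation |
| No rod | item 3 not met | no option fits | excluded after allocation |

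The third row is not far-fetched. The Introduction says that either static or dynamic locking can follow internal compression, whereas item 4 lists internal compression with static locking only.

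Count over the 16 data points: 0 hold the team, assigned group or presentation date; 1 holds the method. The SAP has no statement on intention-to-treat, as-treated or per-protocol analysis, or on crossover.

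**2. Illustrative size, with no true effect**

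Every rate below is an assumption. All arms have the same case mix, so analysis by assigned team gives a difference of 0 throughout.

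*Set 1: every hard case in C crosses to A.* 50 per arm; union 60% in hard and 88% in other fractures; x = share of hard cases.

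- As assigned, any arm: 0.60x + 0.88(1 − x)
- By method, C: 0.88
- By method, A: [50 × as assigned + 50x × 0.60] / (50 + 50x)

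| x | As assigned | A by method | C − A (points) |
|---|---|---|---|
| 5% | 0.866 | (43.3 + 1.5)/52.5 = 0.853 | 2.7 |
| 10% | 0.852 | (42.6 + 3.0)/55 = 0.829 | 5.1 |
| 15% | 0.838 | (41.9 + 4.5)/57.5 = 0.807 | 7.3 |

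*Set 2: only some hard cases in C cross, to B.* Hard share h = 0.30; union 0.95 in easy fractures and p = 0.80 or 0.65 in hard ones; c = fraction of hard cases in C treated by method B.

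- C by method: [0.70 × 0.95 + 0.30(1 − c)p] / [0.70 + 0.30(1 − c)]
- B by method: [0.70 × 0.95 + 0.30(1 + c)p] / [0.70 + 0.30(1 + c)]

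| p | c | Share of arm C crossing | C (%) | B (%) | C − B (points) |
|---|---|---|---|---|---|
| 0.80 | 0.10 | 3% | 90.82 | 90.19 | 0.6 |
| 0.80 | 0.25 | 7.5% | 91.35 | 89.77 | 1.6 |
| 0.80 | 0.50 | 15% | 92.35 | 89.13 | 3.2 |
| 0.65 | 0.10 | 3% | 86.65 | 85.39 | 1.3 |
| 0.65 | 0.25 | 7.5% | 87.70 | 84.53 | 3.2 |
| 0.65 | 0.50 | 15% | 89.71 | 83.26 | 6.5 |

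With c = 0 both arms are at 90.5% (p = 0.80) or 86.0% (p = 0.65), and the difference is 0.

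*If the same patients are excluded instead of moved*, the comparator keeps its as-assigned rate and the gap is smaller. Set 1 gives 0.88 − 0.866 = 1.4 points up to 0.88 − 0.838 = 4.2. Set 2 gives 90.82 − 90.50 = 0.3 points up to 89.71 − 86.00 = 3.7.

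**The case against.** The strongest reply is that this is missing detail and not a faulty rule. The Methodology section does define Groups A, B and C by team. The SAP has not chosen an as-treated analysis; it is silent. Data point 11 does not say whether it means the assigned or the delivered method. The team may be recoverable too: the rotation is strict, complete inpatient records are required, and a master file links names and record numbers.

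Departures may also be few. Inclusion item 2 restricts entry to axially stable fractures that tolerate compression, and the Introduction treats plating as unreasonable without mitigating circumstances. The direction of bias is not given either: departures out of A or B would act the other way.

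Much of this stands, and it limits the point. A reader might infer that the groups are defined by the method used, that the planned analysis is as-treated, or that the assignment is lost for good. The documents support none of these.

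What the reply does not answer is the eligibility rule. Items 3 and 4 are stated conditions, not omissions, and taken literally they remove patients because of what was done after allocation. Nor does it help that the team might be traced, because no step to do so is planned. On the listed fields alone, analysis by assigned team cannot be run where assigned and delivered methods differ, and such patients cannot be counted.

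**Conclusion.** The point holds as a conflict between the allocation rule on one side and the eligibility criteria and data list on the other, with no analysis set in the SAP to settle it. It should be corrected.

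The size of any bias in this trial cannot be stated. If departures are one-way out of C and confined to harder fractures, the illustrations give about 0.6 to 7.3 percentage points in favour of C for crossover, and about 0.3 to 4.2 points for exclusion. With no departures the bias is zero. The upper crossover figure requires every hard case in C to cross over and none to leave A or B, so it should not be read as an estimate for this trial.

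A reader might also infer that analysis by team would give a clean comparison of methods. It would not. The rotation is predictable and not randomised, and each team uses one method, so team and method remain fully confounded. Analysis by assigned team removes bias from selective departures and nothing more.

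**What to change.** 1. **Data Points:** add date and time of presentation and the call team (Red, Green or Blue) at that time.
2. **Inclusion items 3 and 4:** reword as treatment intended at presentation, so that eligibility is settled before assignment and does not depend on what was done in surgery.
3. **Statistical Analysis Plan:** state that the primary analysis compares groups by assigned call team, whatever method was delivered.
4. **Secondary reporting:** give treatment received, the number of departures by group, and an as-treated analysis.

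The cost is small: one set of fields that should follow from the presentation date and the rotation, a few reworded lines, and no change to any patient's care. If no one departed from assignment, the new field lets the sponsor show it.

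The downside is dilution. If a share d of Group C receives the comparator method and the true effect is the same for everyone, analysis by team estimates (1 − d) times that effect: 97% of it at d = 3% and 85% at d = 15%.

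### Two inclusion criteria can be met only after assignment; applied as written they remove assigned patients lost before one year, and the SAP defines no analysis set that keeps them

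*Combined protocol and SAP*

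**What the plan says.** Inclusion Criteria, item 5: "Complete inpatient and outpatient medical records and operative notes". Item 6: "Complete radiographic and clinical follow-up for minimum one year".

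Methodology, on assignment: "Patients who meet inclusion criteria will be assigned to one of the three treatment groups based on the night of presentation". The group is fixed by which of three call teams is on duty. Visits are scheduled as "Follow-up at 6 weeks, 12 weeks, 24 weeks and 52 weeks", and this schedule is one of the matters on which the groups are to be handled alike ("All patients will be treated similarly with respect to"). The Introduction describes the cohort as prospective and consecutive.

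The outcomes in the Primary Hypothesis are rate of union and time to union. The Statistical Analysis Plan gives descriptive statistics, Fisher's exact test for categorical variables, a significance level and the software. On time to union it says: "For continuous variables, a Mann-Whitney U test was utilized with descriptive statistics reported as means and ranges". It names no analysis set, no rule for patients lost to follow-up and no method for censored times.

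**The concern.** An eligibility rule should rest on facts available when the group is assigned. Item 6 is settled a year later, and item 5 depends partly on outpatient records that do not yet exist. Used as inclusion criteria, the two items select patients on something that happens after treatment and may be related to its result. The cohort is then no longer consecutive, and the comparison is no longer between the groups as assigned.

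At stake are both outcomes of the primary hypothesis. The Benefits section also intends the results for counselling patients on "how long they can expect before obtaining radiographic union, and what the potential reoperation rate would be". That use needs each arm's own rate to be right, not only the contrast between arms.

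Time to union has a related gap: Mann-Whitney needs a value for every patient, and a patient who has not united has none. This would be so even if nobody were lost.

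**Working it through.** **Timing.** The plan has no figure to reproduce: it states no sample size, union rate or loss rate. The structural check is a comparison of dates.

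- Assignment: night of presentation (Methodology).
- Item 5 known: after surgery and outpatient visits.
- Item 6 known: one year later.
- Rule that restores a lost patient: none in the Statistical Analysis Plan or elsewhere.

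**Effect on one arm (all inputs assumed).** Let p be true union by 52 weeks, f the share of failures lost and h the share of healed patients lost. Union among those who complete the year is

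p(1 − h) / [p(1 − h) + (1 − p)(1 − f)].

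With p = 0.85:

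- f = 0.25, h = 0: 0.85 / (0.85 + 0.1125) = 88.3%
- f = 0.5, h = 0: 0.85 / (0.85 + 0.075) = 91.9%
- f = 0.1, h = 0.3: 0.595 / (0.595 + 0.135) = 81.5%
- f = h = 0.2: 0.68 / (0.68 + 0.12) = 85.0%

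**Effect on a real difference, same loss in every arm.** With true union of 95% and 85% (10.0 points):

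- f = 0.5, h = 0: 97.4 − 91.9 = 5.5 points
- f = 0.1, h = 0.3: 93.7 − 81.5 = 12.2 points
- f = h = 0.2: 95.0 − 85.0 = 10.0 points

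If the true rates are equal and loss follows the same pattern in every arm, the observed rates are also equal, so a null comparison stays null.

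**Loss in one arm only.** Simulation with two arms, 100 per arm, 85% union in both, deletion of the lost and then Fisher's test at 0.05: it rejects in about 27% of runs if half of one arm's failures are lost, about 4% if 20% are lost regardless of healing, and about 7–8% with 10% of failures and 30% of healed lost.

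**Known outcomes discarded.** Assume union of 10, 45, 75 and 85% by weeks 6, 12, 24 and 52. If 20% of all patients are lost regardless of healing, the share of them already united is 75% when last seen at week 24 (15.0 of 20.0 percentage points), 45% at week 12 (9.0 of 20.0) and 10% at week 6 (2.0 of 20.0).

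**What a censored estimate does.** Suppose half of failures (7.5% of the arm) are last seen at week 12. At week 12, 55% are not united, and 55 − 7.5 = 47.5% remain under observation. Of these, 30 unite by week 24 and 10 more by week 52, leaving 7.5. The Kaplan-Meier estimate of non-union is 0.55 × 7.5/47.5 = 0.087, so estimated union is 91.3% against a true 85%. If instead 20% are lost regardless of healing, the estimate is 85.0%. The bounds are 85.0 to 92.5% in the first case. In the second, with last visit at week 12, the lower bound is 0.8 × 85 + 0.2 × 45 = 77.0% and the upper is 0.8 × 85 + 20 = 88.0%. Both ranges contain 85%.

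**The case against.** The strongest reply is that item 6 is only a follow-up target placed under the wrong heading. No sentence says that a lost patient is deleted. The study has one facility and one visit schedule, and nothing suggests that loss differs by call team. This stands as far as it goes: whether the sponsor would in fact delete patients is not stated. It does not rescue the wording, because the item is numbered among the criteria that decide who is assigned, and no analysis set says otherwise.

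A reader might infer that the comparison is biased, perhaps in favour of internal compression. The documents do not support this. They give no loss rates and no reason for loss to differ by team, and the direction could go either way.

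A reader might also think the remedy is to count every patient lost before union as not united, and to trust a difference only if it keeps its direction across best and worst cases. Both steps can do harm.

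- Counting lost as not united is itself the worst-case bound. In the simulation above it rejects a true null in about 24–67% of runs when 20% of one arm is lost regardless of healing at week 12 or 6 (deletion: about 4%). With 10% of failures and 30% of healed lost at those visits, it rejects in 48–94% (deletion: about 7–8%).
- The direction rule can refuse a real effect. Take true union of 95% and 85%, with 20% of each arm last seen at week 12 and 45% united by then in both. The better arm's lower bound is 0.8 × 95 + 9 = 85.0%, below the other arm's upper bound of 88.0%.

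Two further inferences fail. The Confidentiality section says identifiers "will be stored on a password protected departmental network in a master file"; it does not say the file holds nothing else, so it is no evidence that removed patients could not be traced. Exclusion 8 (bone growth stimulators) does not conflict with data points 16c and 16d, which list exchange rodding and bone grafting.

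**Conclusion.** The wording defect is certain: two inclusion criteria cannot be assessed when patients are assigned. Applied literally, they select the analysed patients on a later event, and nothing in the SAP reverses this. It should be fixed.

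The size of any bias is unknown. Under the assumed loss patterns, an arm's 85% union rate is observed anywhere from 81.5% to 91.9%, and a real 10.0-point difference as 5.5 to 12.2 points. With loss unrelated to healing, neither moves, and mainly precision and the record of losses suffer. Bias between arms under no true difference needs loss that depends on healing and differs by call team, which the documents neither show nor rule out.

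**What to change.** 1. Move items 5 and 6 from eligibility to follow-up targets, and base eligibility on facts known at presentation.
2. Analyse every assigned patient in the group set by call team. Report losses by group with the visit last attended.
3. Count union on any earlier radiograph as union. Analyse time to union, and union by 52 weeks, with a method that keeps lost and non-united patients as censored, in place of Mann-Whitney for time to union. Kaplan-Meier with log-rank would serve; an interval-censored method suits the four fixed visits better.
4. Report best/worst-case bounds for 52-week union as sensitivity analyses only. Do not make lost = not united the primary rule, and do not require the difference to keep its direction across the bounds.

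The cost is protocol and SAP wording, a table of losses and some extra analysis; if the named SPSS version lacks the chosen test, other software must be named. The SAP is partly in the past tense. If the analysis has already been done, steps 2 to 4 can be applied wherever the records of removed patients still exist.

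The downside is that some outcomes are censored, and the censored estimate is too high when failures leave early (91.3% instead of 85% in the example). The log-rank test does not cure this: with half of one arm's failures lost, its simulated error rate was 0.062, 0.119 and 0.200 for last visits at week 24, 12 and 6. With 20% lost regardless of healing it was 0.056, 0.053 and 0.053. That is why the bounds belong beside the main result.
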